Appendix III: Semi-structured Questionnaires – Assessment of the intuitiveness of AirWaze features

The AirWaze study is focused on researching the intuitiveness of the different AirWaze features. These semi-structured questionnaires will be conducted after every 4 procedures per operator.

The AirWaze software feature is intuitive (from a clinical perspective) to use:

AirWaze feature	1 Strongly disagree	2 Disagree	3 Neutral	4 Agree	5 Strongly agree
Advanced planning software					
Augmented fluoroscopy					
Automatic device detection					
Directional guidance software					
CBCT-FluoroSweep					

Additional questions:

1.

Is the information displayed visible/readable? If not, what could be improved?

a.

Yes

b.

No, because

c.

Other,
2.

Was the relevant information that you need in the decision-making visible? If yes, what was most important information for you? If not, what could be improved?

a.

Yes,

b.

No, because

c.

Other,
3.

Based on your experience, what aspects of the AirWaze software solution are most valuable to you?

.....
4.

What is still missing in the AirWaze software solution and/or what feature should still be further improved?

.....

IGT Systems	Feasibility Clinical Investigation Protocol AirWaze – easy and advanced tools for CBCT guided lung interventions	Doc ID: XCY607-130895 Rev: 04 Date: 2024-Jun-19 Page 44 of 56
-------------	--	--

5. What are the top three **advantages** that you experienced when using the AirWaze investigational device?
- a. _____
 - b. _____
 - c. _____
6. What are the first three **disadvantages** that come to your mind when using the AirWaze investigational device?
- a. _____
 - b. _____
 - c. _____
7. Any other comment?
-

IGT Systems	Feasibility Clinical Investigation Protocol AirWaze – easy and advanced tools for CBCT guided lung interventions	Doc ID: XCY607-130895 Rev: 04 Date: 2024-Jun-19 Page 45 of 56
-------------	--	--

Appendix IV: Semi-structured Questionnaire for quantitative and qualitative assessment of the developed algorithms

The quality of the algorithms will be assessed through this questionnaire and will be conducted after every procedure per operator.

Advanced planning software

The advanced planning software contains two major algorithms for: 1) segmentation of the bronchial tree, and 2) image registration.

1. Segmentation of the bronchial tree

The segmentation of the bronchial tree is rated independently from the location of the lesion.

- **1:** Only the trachea, right/left main bronchus, and bronchus intermedius are segmented.
- **2:** RB1 t/m RB10 and LB1 t/m LB10 are segmented.
- **3:** Few (1-2) branches beyond the RB or LB branches are segmented.
- **4:** More (≥ 3) branches beyond the RB or LB branches are segmented to 2 cm from the pleura.
- **5:** Bronchioles on a distance < 2 cm from the pleura are segmented.

a. Please rate the quality of the segmented bronchial tree on the preoperative CT scan:

1	2	3	4	5	Segmentation failed
Please elaborate:					

b. Based on the segmentation of the bronchial tree, is there a bronchus sign?

- a. Yes, there is a bronchus sign.
- b. No, there is no bronchus sign.
- c. Cannot be determined, because insufficient level of bronchial tree segmentation.

c. If not sufficient level of bronchial tree segmentation: Do you have any clue what was the origin of the unacceptable segmentation?

.....

d. Did you notice/experience any glitches? If yes, please elaborate.

.....

IGT Systems	Feasibility Clinical Investigation Protocol	Doc ID: XCY607-130895
	AirWaze – easy and advanced tools for CBCT guided lung interventions	Rev: 04 Date: 2024-Jun-19 Page 46 of 56

2. Image registration

The image registration is bad if the registration around the target of interest shows large errors. The image registration is excellent if the images are registered accurately around the target of interest.

The image registration is evaluated between the different CBCT-scans made during the procedure. The most recent acquired image is the fixed image, and the older acquired image is the moving image. In future AirWaze implementation, it is desirable to replace the CBCT with the low-dose CBCT-FS. In those procedures one normal-dose CBCT is acquired. The navigation trajectory and lesion segmentations are moved from the CBCT image to the CBCT-FS images. If there are less CBCT(-FS) performed, the image registration is addressed as N/A.

- a. Please rate the quality of the image registration at the location of the lesion:

Image registration between moved and fixed scans	1 Bad	2 Poor	3 Fair	4 Good	5 Excellent	Image registration failed
Pre-op CT --> CBCT1						
CBCT1 --> CBCT-FS1						
..... -->						
..... -->						
..... -->						

- b. If not acceptable level of image registration: Can it be corrected manually? And do you have any clue for the origin of the unacceptable levels of image registration?

.....

- c. Did you notice/experience any glitches?

.....

Automatic device detection

The automatic device detection is poor if the device is barely or wrongly detected. The automatic device detection is excellent if the device is detected completely.

1. Please rate the quality of the automatic catheter detection during the procedure after acquiring a CBCT scan:

Scan	1 Bad	2 Poor	3 Fair	4 Good	5 Excellent	Automatic device detection failed
CBCT1						
CBCT-FS1						
.....						
.....						
.....						

IGT Systems	Feasibility Clinical Investigation Protocol AirWaze – easy and advanced tools for CBCT guided lung interventions	Doc ID: XCY607-130895 Rev: 04 Date: 2024-Jun-19 Page 47 of 56
-------------	--	--

2. If not acceptable level of automatic device detection. What is in your view the origin of the unacceptable levels of automatic device detection?

.....

3. Did you notice/experience any glitches? If yes, please elaborate.

.....

IGT Systems	Feasibility Clinical Investigation Protocol AirWaze – easy and advanced tools for CBCT guided lung interventions	Doc ID: XCY607-130895 Rev: 04 Date: 2024-Jun-19 Page 48 of 56
-------------	--	--

Appendix V: AirWaze Procedural Analysis

PART A: Pre-Procedural Planning

OPERATOR:

STUDY CODE:

1) Time start planning? (Measured from opening preoperative CT scan OR from opening AirWaze)			... : ...
2) Catheter curvature for navigating to target lesion?	 180 °	 Medial	 Other, please specify...
3) Bronchus sign?	 Yes	 No	 Maybe
4) Pulmonary branch for navigation	 RB 1  RB 2  RB 3  RB 4  RB 5  RB 6  RB 7  RB 8  RB 9  RB 10	 LB 1+2  LB 3  LB 4  LB 5  LB 6  LB 8  LB 9  LB 10  Anatomical deviation:	
5) How would you describe your planned trajectory? Be as specific as possible.			
..... (In the post-procedural questionnaire, you will evaluate whether your trajectory prediction was accurate).			

IGT Systems	Feasibility Clinical Investigation Protocol AirWaze – easy and advanced tools for CBCT guided lung interventions	Doc ID: XCY607-130895 Rev: 04 Date: 2024-Jun-19 Page 49 of 56
-------------	--	--

6) Time end planning? (Measured till the closing of the pre-operative CT scan during the pre-procedural planning (e.g. control group) OR till closing AirWaze).												
7) Total planning time? minutes of planning time												
8) How complex was the lesion localization and trajectory planning, to the first target lesion?	Low	0	1	2	3	4	5	6	7	8	9	High 10
9) How confident are you that you have accurately localized and planned the trajectory to the first pulmonary target lesion?	Low	0	1	2	3	4	5	6	7	8	9	High 10
10) Based on the planning, how complex do you expect the CBCT-guided bronchoscopy towards the first lesion to be?	Low	0	1	2	3	4	5	6	7	8	9	High 10
11) Based on the planning, how confident are you that you are going to successfully reach the first pulmonary target lesion?	Low	0	1	2	3	4	5	6	7	8	9	High 10
12) Comments regarding the pre-procedural planning? (e.g. quality (PET-)CT, software bugs, distractions)												

IGT Systems	Feasibility Clinical Investigation Protocol	Doc ID: XCY607-130895
	AirWaze – easy and advanced tools for CBCT guided lung interventions	Rev: 04
		Date: 2024-Jun-19
		Page 50 of 56

PART B: Intra-procedural navigation SURG-TLX Form

OPERATOR:

STUDY CODE:

1) How would you rank the demands related to the navigation to the first target pulmonary lesion from less important to most important demand (scale 0 to 5)? You are only allowed to use every number once.		 Mental demand:		 Task complexity:																			
		 Physical demand:		 Situational stress:																			
		 Temporal demand:		 Distractions:																			
		0		5		10		15		20													
1A) Mental demands: How mentally fatiguing was the navigation ?	Very Low																						Very High
1B) Physical demands: How physically fatiguing was the navigation ?	Very Low																						Very High
1C) Temporal demands: How hurried or rushed was the pace of the navigation ?	Very Low																						Very High
1D) Task complexity: How complex was the navigation ?	Not Very Complex																						Very Complex
1E) Situational stress: How anxious did you feel while performing the navigation ?	Not Very Anxious																						Very Anxious
1F) Distractions: How distracting was the operating work environment during the navigation ?	Not Very																						Very

IGT Systems	Feasibility Clinical Investigation Protocol AirWaze – easy and advanced tools for CBCT guided lung interventions	Doc ID: XCY607-130895 Rev: 04 Date: 2024-Jun-19 Page 51 of 56
-------------	--	--

PART C: End-procedural Form

OPERATOR:

STUDY CODE:

1) Was the lesion targeted successfully?	 Yes	 No
2) Curvature catheter (for target lesion)?	 Medial	 180 °  Other
3) Does the performed navigation trajectory match the trajectory as planned in the pre-procedural form?	 Yes	 No
4) Which situation matches the performed navigation trajectory compared to the pre-procedural trajectory of the operator? The performed trajectory	 fully matches the planned trajectory.  bifurcates different late in the navigation.  bifurcates different early in the navigation.  is mispositioned.  has a transparenchymal route instead of an endobronchial route.  has an endobronchial route instead of a transparenchymal route.  does not reach the target at all.  is hard to compare with the planned trajectory, because of atelectasis or displacement of the lesion.  Other,	
5) To what extent did the planning contribute to reaching the first target lesion?	
Low
 
0 1 2 3 4 5 6 7 8 9 High
	
6) Effective dose fluoroscopy and time fluoroscopy radiation during navigation and confirmation of first target lesion? mSv Gy*cm ² fluoroscopy time (s)
7) Effective dose CBCT and No. of CBCT scans during navigation and confirmation of first target lesion? mSv Gy*cm ² CBCT scans (n)
8) Effective dose CBCT-FS and No. of CBCT-FS scans during navigation and confirmation of first target lesion? mSv Gy*cm ² CBCT- FS scans (n)

IGT Systems	Feasibility Clinical Investigation Protocol AirWaze – easy and advanced tools for CBCT guided lung interventions	Doc ID: XCY607-130895 Rev: 04 Date: 2024-Jun-19 Page 52 of 56
-------------	--	--

9) Average (scattered) radiation dose staff (main operator)?		 mSv (ring dosimeter) mSv (chest dosimeter)
9) ROSE pathology outcome	
○ Malignant○ Atypical cells	
○ Benign specific○ Benign non-specific○ Not representative		
10) Patient Safety issues? (To be reported in the Clinical Study End Report)	
○ Yes, adverse events, namely:○ Yes, adverse device effects namely:○ Yes, device deficiencies, namely:			
12) Comments regarding the AirWaze software tools during the procedure? (Quality CBCT or CBCT-FS scans, software bugs, distractions in OR, other)				

IGT Systems	Feasibility Clinical Investigation Protocol	Doc ID: XCY607-130895
	AirWaze – easy and advanced tools for CBCT guided lung interventions	Rev: 04 Date: 2024-Jun-19 Page 53 of 56

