- The cognitive load of pulmonologists during the navigation towards the first lesion will be measured with the Surgical Task Load Index (SURG-TLX) which is a validated method for measuring cognitive load. The questionnaire is asked after tool-in-lesion confirmation (either rEBUS, CBCT, or CBCT-FS) ^{12,16,17} (Appendix V).
- Radiation exposure for patients will be measured in effective dose (mSv) and DAP (Gy·cm²) per procedure including fluoroscopy, CBCT and CBCT-FS radiation dose. The fluoroscopy time (minutes) will be measured as well (Appendix V).
- Radiation exposure for the staff is measured in an average scattered effective dose (mSv) per procedure at hand and chest (Appendix V).
- Report all adverse events (including but not limited to pneumonia, pneumothorax, bleeding/hemorrhage).
- Report all adverse device effects.
- Report all device deficiencies. Device deficiencies that could have led to an SAE need to be reported in the Clinical Study End Report.

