8.7.6. Secondary objective: Radiation exposure for patients and staff

Objective

To assess the radiation exposure for patients and staff.

Endpoint

- Radiation exposure for patients will be measured in effective dose (mSv) and DAP (Gy·cm²) per procedure including disaggregated fluoroscopy, CBCT and CBCT-FS scan dose. Also, the fluoroscopy time (minutes) will be measured.
- Radiation exposure for staff is measured in an average scattered effective dose (mSv) per procedure at hand and chest.

Analysis

- The radiation exposure for patients will be expressed in an average effective dose and DAP per procedure. The average effective dose and DAP will be higher compared to conventional procedures, but the increase in radiation dose will be relatively low (Appendix VI: Radiation Dose of CBCT-guided NB). The analysis includes a calculation of the mean, medians and standard deviations for effective dose and DAP per procedure.
- The radiation exposure for staff will be expressed in the average effective dose at hand and chest. The average effective dose and DAP will be higher compared to conventional procedures, but this increase in radiation dose will be relatively low (Appendix VI: Radiation Dose of CBCT-guided NB). The analysis includes a calculation of the mean, medians and standard deviations for effective dose at hand and chest.

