The estimated radiation exposure of the AirWaze study is depicted in Table 7.

- Radiation exposure assumptions:
 - Verhoeven *et al.* has reported the radiation exposure of CBCT-guided navigation bronchoscopy for biopsy of PPNs. An average fluoroscopy time of 935 seconds was used for real-time navigation and sampling guidance. The average total DAP for these 935 seconds was 2.2 Gy·cm².
 - It is expected that the implementation of AirWaze CBCT-FS will reduce the fluoroscopy time and thus the overall DAP. This benefit of an expected reduction in fluoroscopy time is not considered in the calculations as depicted in Table 7.
- AirWaze and CBCT-FS are implemented for testing the clinical and technical feasibility. The first performed scan during a procedure is a conventional CBCT. In case additional scans are required, a CBCT-FS scan is performed on top of the conventional imaging protocol. A comparison between the additional CBCT and CBCT-FS is then made. The DAP per CBCT-FS acquisition is less than 1.45 Gy·cm² based on preclinical studies.

IGT Systems	Feasibility Clinical Investigation Protocol AirWaze – easy and advanced tools for CBCT guided lung interventions	Doc ID: XCY607-130895 Rev: 04 Date: 2024-Jun-19 Page 54 of 56
-------------	--	--

Table 7. Expected estimated radiation exposure during this Feasibility Clinical Investigation

	Low Dose Fluoroscopy		CBCT			CBCT-FS*		Total DAP (Gy·cm ²)
	DAP (Gy·cm ²)	Time (s)	Protocol	DAP (Gy·cm ²) / acq.	Acqs.	DAP (Gy·cm ²) / acq.	Acquisitions	
CBCT-NB w/o AirWaze	2.2	935	Normal dose	11.55	1	-	-	20.8-37.8
			Low dose	8.02	1-3			
Study (n=22)	2.2	935	Normal dose	11.55	1	-	-	22.3-42.2
			Low dose	8.02	1-3	1.45	1-3	

* The number of CBCT-FS scans are expected to be equal to the number of additional low dose CBCT scans performed (=total number of CBCT minus one).

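### Patient dose is defined per procedure, but the Appendix V form records it only up to confirmation of the first lesion; separately, both lower ends in Table 7 are mis-summed

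*Combined protocol and SAP*

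**What the plan says.** Section 8.7.6 measures patient dose "per procedure including disaggregated fluoroscopy, CBCT and CBCT-FS scan dose", together with fluoroscopy time, and sets the summary: "The radiation exposure for patients will be expressed in an average effective dose and DAP per procedure". Section 7.1.1 gives the same endpoint and points to the form: "The fluoroscopy time (minutes) will be measured as well (Appendix V".

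The patient-dose fields on that form are Appendix V Part C items 6, 7 and 8:

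- Item 6: "Effective dose fluoroscopy and time fluoroscopy radiation during navigation and confirmation of first target lesion"
- Item 7: "Effective dose CBCT and No. of CBCT scans during navigation and confirmation of first target lesion"
- Item 8: "Effective dose CBCT-FS and No. of CBCT-FS scans during navigation and confirmation of first target lesion"

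Each has spaces for mSv and Gy·cm². The staff-dose item that follows has no first-lesion limit.

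On interpretation, section 8.7.6 states: "The average effective dose and DAP will be higher compared to conventional procedures, but the increase in radiation dose will be relatively low". It refers to Appendix VI, which describes its fluoroscopy benchmark thus: "An average fluoroscopy time of 935 seconds was used for real-time navigation and sampling guidance". Table 7 in Appendix VI then projects total DAP at 20.8-37.8 Gy·cm² without AirWaze and 22.3-42.2 Gy·cm² in the study.

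**The concern.** The endpoint and the form cover different parts of the procedure. Section 7.4 places tissue sampling after tool-in-lesion confirmation, so fluoroscopy used for sampling lies outside items 6 to 8 even when there is only one lesion. The repeated references to a first lesion imply that some procedures will have another, and none of its fluoroscopy, CBCT or CBCT-FS dose has a field. The comparator has neither limit.

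Section 5 accepts extra radiation as a known consequence of pairing CBCT with CBCT-FS and calls its impact minimal. The patient-dose endpoint is the check on that statement. A part-procedure dose read against a whole-procedure benchmark understates the contrast, and no later analysis can recover dose that was not recorded.

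Table 7, which supplies the projected comparison, also has a summing error. That is a separate matter and needs its own check.

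**Working it through.** **Inputs.** All are from Appendix VI, in Gy·cm²: fluoroscopy 2.2 per procedure; one normal-dose CBCT at 11.55; k low-dose CBCTs at 8.02 each, k = 1 to 3; one CBCT-FS per low-dose CBCT at 1.45 (given as an upper bound).

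**1. Table 7 from its own inputs**

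Conventional = 2.2 + 11.55 + 8.02k. Study = conventional + 1.45k.

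| k | Conventional | Printed | Study | Printed |
|---|---|---|---|---|
| 1 | 21.77 | 20.8 | 23.22 | 22.3 |
| 3 | 37.81 | 37.8 | 42.16 | 42.2 |

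Both upper ends reproduce and both lower ends do not. They are too low by 21.77 − 20.8 = 0.97 and 23.22 − 22.3 = 0.92. It looks like one slip carried forward, since 20.8 + 1.45 = 22.25. Leaving out fluoroscopy (19.57) or using the text's 11.6 in place of 11.55 (21.82) does not give 20.8 either.

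The increase is 1.45k, which is 1.45 to 4.35: 1.45/21.77 = 6.7% and 4.35/37.81 = 11.5% of the re-summed conventional total. The printed ranges imply 22.3 − 20.8 = 1.5 and 42.2 − 37.8 = 4.4, so the slip leaves the increase unchanged apart from rounding.

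**2. Scope of the benchmark**

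Table 6, normal-dose row: 2.2 + 11.55 × 2.25 = 28.19, printed 28.2. The total is therefore fluoroscopy plus all CBCT acquisitions in the procedure, and the text says that fluoroscopy includes sampling. (The low-dose row gives 2.2 + 8.02 × 2.93 = 25.70 against 25.4. A product of two means need not equal a mean total, so I do not call that an error.)

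**3. Shortfall with a single lesion**

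CBCT makes up 19.57/21.77 = 90% to 35.61/37.81 = 94% of the conventional total, and scans for first-lesion navigation and confirmation are inside items 7 and 8. What clearly falls outside is fluoroscopy after confirmation. The documents do not give sampling's share s of the 2.2. As an assumption, take s = 10 to 75%:

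- 0.10 × 2.2 = 0.22, and 0.75 × 2.2 = 1.65.
- Against the study totals, this runs from 0.22/42.16 = 0.5% to 1.65/23.22 = 7.1%.

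**4. Shortfall with a further lesion**

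Each low-dose CBCT and CBCT-FS pair adds 8.02 + 1.45 = 9.47. Section 7.4 allows confirmation by rEBUS or ROSE, so a further lesion might need no pair. Assuming 0 to 3 pairs, the scans left out of that procedure total 0 to 28.41, plus any fluoroscopy.

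The effect on the trial mean depends on how often this happens, and no rate is given for this trial. Section 4.2 reports 59 lesions in 52 subjects with version 1.0 of the device, or 7/52 = 0.135 extra lesions per subject. If that rate applied here and every extra lesion were imaged in the same session, the mean would lose 0 to 0.135 × 28.41 = 3.8. This is an illustration, not an estimate.

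**The case against.** The strongest reply is that little depends on this.

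- Section 8.7 makes the secondary objectives descriptive with no performance requirements. Section 8.7.6 plans means, medians and standard deviations only, and the comparator is a wide projection rather than a control arm. This stands and limits the severity.
- Item 8 records CBCT-FS dose and scan count separately, so the dose that CBCT-FS adds at the first lesion is measured without any benchmark. This also stands. It does not cover CBCT-FS at further lesions or supply the per-procedure total.
- Section 9 says the e-CRF collects procedure-related information without listing the fields, so whole-procedure dose may be recorded elsewhere. That is possible, but 7.1.1 names Appendix V and no other patient-dose field is shown. If another source exists, the protocol should name it.

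A reader might infer that the Table 7 slip adds to the understatement of dose. It does not: a comparator printed too low makes observed dose look higher against it, and the study row moves by almost the same amount.

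A reader might also infer that the omitted dose is about as large as the expected increase, so that the increase would vanish or turn into a reduction. The documents do not show this. It needs an unsourced sampling share, a multi-lesion rate borrowed from another study, and an assumed number of scans for each further lesion.

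**Conclusion.** There are two separate errors. First, the form as worded does not supply the endpoint as defined. The mismatch and its direction are certain from the text: the recorded dose is at or below the per-procedure dose. Its size is not known. With one lesion it is 0.2 to 1.7 Gy·cm² on the assumed 10 to 75% sampling share, against an expected increase of 1.45 to 4.35. With a further imaged lesion it is larger by an amount the documents do not determine. The effect is on a descriptive contrast, not on a test or a decision rule.

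Second, the lower ends of Table 7 are wrong on their own inputs by a little under 1 Gy·cm² each. This is an arithmetic slip with no bearing on the first error. The study row is also labelled n=22, while section 8.2 plans 37 patients; the label enters no calculation.

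Severity: minor to moderate.

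**What to change.** - **Form.** Reword Appendix V Part C items 6 to 8 to ask for whole-procedure totals for fluoroscopy (dose and time), CBCT and CBCT-FS. Keep the first-lesion values as extra fields. Use one unit for fluoroscopy time: the endpoint gives minutes and the form gives seconds.
- **Analysis.** State in 8.7.6 that the totals are what is summarised, and that any comparison with Appendix VI uses figures covering the same parts of the procedure. If totals are already held elsewhere in the e-CRF, name that source in 7.1.1 instead.
- **Patients already treated.** Enrolment began in October 2023, so check now whether whole-procedure totals can be retrieved. The documents do not say that they can. Where they cannot, report those patients as first-lesion dose only and do not pool them with the totals.
- **Table 7.** Change 20.8 to 21.8 and 22.3 to 23.2, leave 37.8 and 42.2 as they are, and update the n=22 label to the planned number of subjects.

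The cost is one more set of form fields, a retrieval check, and a reported mean dose that will probably be higher.
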